10.1. Schedule of Events

The start of the study is defined as the date the subject first signs the informed consent. The completion of the study for each subject is defined as the completion of the final study visit. Subjects that do not qualify for the study prior to the first PTNM therapy session will be exited from the study. The completion of the study is defined as the completion of the Final Study Report and closure of all sites.

Confidential

Figure 1-1: Study Procedures illustrates required study procedure:

Figure 1-1: Study Procedures

Confidential

A detailed table of the study procedures, presenting the type of procedure required at each visit, is presented in Table 1-1.

Table 1-1: Study Procedures

Procedures	Enrollment/ Baseline Visit	PTNM Session #1	PTNM Session #2	PTNM Session #3	PTNM Session #4	PTNM Session #5	PTNM Session #6	PTNM Session #7	PTNM Session #8	PTNM Session #9	PTNM Session #10	PTNM Session #11	PTNM Session #12	Final Study Visit
Informed Consent Form	X													
Inclusion/Exclusion	X	X												
Pregnancy Test*	X*													
Reportable Medical History	X													
Distribute Urinary Voiding Diary	X	X			X				X				X	
Distribute Fecal Incontinence Diary**	X												X	
Collect Urinary Voiding Diary		X***	X			X			X					X
Collect Fecal Incontinence Diary **		X												X
OABq Questionnaire	X		X			X				X				X
UPS Questionnaire	X		X			X				X				X
PPBC Questionnaire	X		X			X				X				X
PGI-I Questionnaire														X
SAGA Questionnaire	X													X
Conservative Therapies for OAB	X	X	X	X	X	X	X	X	X	X	X	X	X	X
AE Review	X	X	X	X	X	X	X	X	X	X	X	X	X	X
OAB Medication Review	X	X	X	X	X	X	X	X	X	X	X	X	X	X

*For women of child bearing potential to be completed prior to the first PTNM therapy session

**Fecal incontinence Diary (7-day) is recommended for subjects with dual incontinence

***Qualification diary must be reviewed to confirm eligibility prior to beginning first PTNM therapy session

Confidential

10.2. Subject Screening

Subjects may be recruited through the investigator's practice and referring physicians.

Potential subjects may be identified through chart reviews or as new or existing patients attend clinic visits. If subjects are recruited from outside the investigator's practice, sites are to ensure that appropriate release for access to the subject's records (paper and/or electronic) is obtained. Any subject recruitment materials disseminated to subjects (advertisements, handouts, posters, social media) must be approved by the IRB prior to use.

Recruited subjects will be screened by the Principal Investigator or authorized site personnel by reviewing the study's inclusion and exclusion criteria. All subjects must be consented in accordance with the protocol prior to any study-specific procedures.

As part of the inclusion/exclusion evaluation, the MESA urinary incontinence questionnaire will be used to exclude predominant stress incontinence. If the Investigator's assessment differs from the results of the MESA questionnaire, rationale must be documented to explain the decision to enroll the subject.

10.3. Prior and Concomitant Medications

Subjects may not be enrolled if they have had any prior treatment with anticholinergic/antimuscarinic or beta 3-agonist medications to treat OAB.

10.4. Subject Consent

The informed consent process will be performed in accordance with the ethical principles that have their origin in the Declaration of Helsinki and with 21CFR§50 Protection of Human Subjects.

Prior to entering the study, the Principal Investigator or qualified designee will explain to each subject the purpose and nature of the study, procedures, expected study duration, available alternative therapies, and the benefits and risks involved with study participation and the potential treatment. Subjects will be given a copy of the IRB-approved ICF and will have time to review the document and to ask questions and will be informed of their right to withdraw from the study at any time without prejudice; ICFs will be provided in a language understandable to the subject. After this explanation and before any study-specific procedures have been performed, the subject will voluntarily sign and date the ICF. Prior to participation in the study, the subject will receive a copy of the signed and dated written informed consent and any other written information provided to the subject.

The Principal Investigator or qualified (delegated) designee will document the informed consent process, including the date of consent and name of the person conducting the consent process in the subject's medical record. A copy of the signed ICF will also be placed in the subject's medical record.

10.5. Medication Compliance

Subjects eligible to participate must be OAB drug naïve.

If a subject starts an OAB medication prior to starting the PTNM therapy sessions, they should be considered ineligible for the study and should be exited.

Confidential

If a subject starts anticholinergic/antimuscarinic or beta 3-agonist medications to treat OAB following their first PTNM therapy session a deviation form will be completed and this medication will be captured on the OAB medication form.

Medications used to treat reportable adverse events will be documented as "interventions" on the adverse event case report form.

10.6. Assessment of Efficacy

Subject assessments will be performed by appropriately trained, qualified and delegated site personnel according to the usual practices of the site.

Medical History and Demographics

Assessments will be completed and reported on the eCRF.

Urinary Voiding Diary

Symptoms related to OAB will be evaluated using paper voiding diaries. Subjects will be trained to complete the urinary voiding diaries for 3-days as part of the baseline procedures and instructed to start the voiding diary approximately 1 day after PTNM Session #1, #4, #8 and #12. These voiding diaries will then be collected at the next following PTNM Session. Every effort should be made to remind subjects of the importance of real-time diary completion.

Voiding diary data will be used to verify study inclusion criteria for UUI episodes at baseline. Diaries will also be used for comparison to baseline for the primary study endpoint of UUI, secondary study endpoint of urgency frequency (UF) and additional measures related to urgency, nocturia and nighttime frequency. As clinically defined, nocturia will be measured as the number of times the subject is woken from sleep to void.¹⁷ Nighttime frequency will be defined as number of voids during nighttime sleep.¹⁷

Fecal Incontinence Diary

It is recommended that subjects with dual incontinence complete a 7-day fecal incontinence diary during baseline procedures and after 12 PTNM therapy sessions.

PTNM Therapy Sessions

Subjects will receive 12 weekly PTNM therapy sessions following the enrollment/baseline visit.

Assessments for Quality of Life Measures

Subjects will complete the study questionnaires confidentially on paper forms without site personnel consultation and these data will be entered to OC/RDC by site personnel. Questionnaires should be completed prior to the initiation of the PTNM therapy session. Site personnel are encouraged to review forms for completeness.

Overactive Bladder Quality of Life Questionnaire (OABq)

The Overactive Bladder Quality of Life Questionnaire (OABq) is a 33-item questionnaire that was developed to assess symptom bother and the impact of overactive bladder (OAB) on health-related

Confidential

quality of life (HRQL).¹⁸ The questionnaire used in the current study includes a 1-week recall for symptom assessment.

Urgency Perception Scale (UPS)

The Urgency Perception Scale (UPS) is a single item questionnaire measure of perceived urinary urgency with three response options.^{19,20}

Self-Assessment Goal Achievement Questionnaire (SAGA)

Patient attainment goals have been used throughout the literature in order to determine if patients are reaching pre-determined goals.^{21,22} The Self-Assessment Goal Achievement (SAGA) questionnaire is a tool designed to help patients with lower urinary tract symptoms assess goal achievement.²³ The SAGA questionnaire allows for the patient to rank, in order of importance for standard urology symptom goals using a scale of 0-5 and allows for other personal goals to be included. After treatment has been completed, the patient then completes the follow-up assessment which includes a scale of -2 to 2 to report on achievement of each symptom goal and personal goal(s). The questionnaire includes an assessment question of "Overall, to what extent have you achieved your goals" on a scale of 0-4.

Patient Perception of Bladder Condition (PPBC)

The Patient Perception of Bladder Condition (PPBC) is a single-item, 6-point scale that asks patients to rate their subjective impression of their current bladder problems.^{24,25}

Patient Global Impression of Improvement (PGI-I)

Overall impression for improvement is evaluated using the Patient Global Impression of Improvement (PGI-I)²⁶⁻²⁸ which is a single question asking the patient to rate their urinary condition now as compared with prior to beginning treatment on a scale from 1 (very much better) to 7 (very much worse).

10.7. Assessment of Safety

Subjects will be assessed for potential reportable adverse events that are reportable under the study protocol at each study visit.

10.8. Recording Data

This study will be conducted using a remote data capture system. The Oracle Clinical Remote Data Capture (RDC) system which allows the study centers to enter study data into the sponsor's database over a secure internet connection, will be used to capture study required Case Report Form (CRF) information. Paper CRFs will be utilized for voiding diaries and subject questionnaires only; however data will be entered to the database by site personnel. Subjects will complete the study questionnaires confidentially on paper forms without site personnel consultation and these data will be entered to OC/RDC by site personnel. Electronic CRFs (eCRFs) will be provided by the sponsor; required data will be

Confidential

taken from source documents and directly entered into the study database via the CRFs by the site personnel, in accordance with applicable regulations.

Subject voiding diaries and questionnaires are to be completed only by the subject. Representatives from the research site may not make changes to the diaries or questionnaires with the exception of administrative entries and clarification on source documentation.

The Principal or Sub-Investigator, or an individual delegated by the Principal Investigator on the Delegation of Authority and Signature Form, is responsible for documenting and entering data for the study on the eCRFs. The Principal Investigator or Sub-Investigator is required to approve all data on CRFs via electronic signature.

10.9. Deviation Handling

Protocol deviations are digressions from the written protocol defined as an event where the clinical investigator or site personnel did not conduct protocol-required procedures according to the study protocol. Protocol deviations are to be preapproved by Medtronic study personnel and the IRB (as required) unless the deviation is necessary to protect the health, safety, or welfare of a subject in an emergency situation. The investigator or delegated site personnel should immediately contact the designated Medtronic study personnel to discuss the impact of the potential deviation; prior approval of deviations should be documented. Prior approval is generally not required if the deviation is due to an emergency circumstance or an unforeseen circumstance that is beyond the investigator's control; however, these deviations should be reported to Medtronic and the IRB (as required) after site personnel become aware of the deviation. All protocol deviations must be reported on the Protocol Deviation eCRF after the site's awareness of the deviation.

The sponsor may choose to terminate the study at a site for failure to follow the written protocol and investigator agreement. If this occurs, the Investigator and IRB will be notified in writing of the reasons for the termination.

10.10. Subject Withdrawal or Discontinuation

Subjects are free to voluntarily withdraw from the study at any time and for any reason. The investigator can withdraw a subject from the study at any time and for any reason. Withdrawn or exited subjects will be followed under normal medical practice.

Examples of reasons for study discontinuation include, but are not limited to, those listed below:

- If the subject does not meet eligibility criteria of at least 3 UUI episodes of mild, moderate, or severe urgency demonstrated on a 3-day urinary voiding diary
- Subject death
- Subject lost to follow-up
- Subject voluntarily withdraws from the study
- Subject becomes pregnant
- Investigator terminates the subject's participation in the study due to lack of compliance, violation of/change in eligibility criteria

Confidential

- Any clinical laboratory abnormality, inter-current illness, or other medical condition or situation occurs such that continued study participation would not be in the best interest of the subject.
- Subject is not a candidate for PTNM therapy
- Normal study completion

Prior to deeming a subject lost to follow-up, telephone calls must be documented in the subject's medical record. If a minimum of three attempts to contact the subject have failed (e.g. phone and mailed letter), and no response is received, the site should exit the subject and complete the Study Discontinuation eCRF.

When a subject is withdrawn from the study, the Study Discontinuation eCRF is to be completed and should include detailed notes as to why the subject was withdrawn from the study (e.g., discomfort, lack of efficacy, diary too burdensome). There is no further medical care provided under the study after a subject exits from the study.

11. Risks and Benefits

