At the weekly follow-up visits, any OAB medication(s), conservative therapies for OAB and reportable adverse events will be collected from the subject. Subjects will then complete a PTNM therapy session with the NURO device used in accordance with the NURO system Instructions for Use.

Three-day voiding diaries will be provided to the subjects to be started approximately one day after PTNM Session #1, PTNM Session #4, PTNM Session #8, and PTNM Session #12.

At PTNM Session #2, PTNM Session #5 and PTNM Session #9, and the final visit subjects will return their completed 3-day urinary voiding diary and complete OABq, UPS and PPBC questionnaires. Subjects are required to complete the questionnaires prior to the PTNM therapy session. Subjects will then complete a PTNM therapy session with the NURO device used in accordance with the NURO system Instructions for Use.

After PTNM Session #12, a 3-day urinary voiding diary will be provided for the subject to start approximately one day after the therapy session. Subjects who have dual incontinence that completed 7-day fecal incontinence diary at baseline be provided with a final 7-day fecal incontinence diary.

Final Study Visit (1 Week ± 3 days)

At the final study visit, the completed final 3-day urinary voiding diary, 7-day fecal incontinence diary (if applicable), any OAB medication(s), conservative therapies for OAB and reportable adverse events will be collected from the subject. Subjects will complete the following required questionnaires: OABq, UPS, PPBC, PGI-I, and SAGA. Following collection of all study-related data, the subject will be exited from the study.

[figure not shown]

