14.1. General Statistical Considerations

14.1.1. Study Sample Size Justification

This study is to evaluate the reduction from baseline in the number of UUI episodes per day after the 12th PTNM therapy session. The OrBIT trial by Peters et al (2009)⁵ compared the effectiveness of PTNS to extended-release tolterodine. This study reported an average reduction of UUI at 12 weeks compared to baseline in the PTNS arm was 1 episode per day with a standard deviation of 2.2. The following assumptions were used for the sample size calculations: reduction of 0.75 UUI episodes/day from baseline, one-sample t-test with two-sided $\alpha=0.05$, 90% power, and an estimated standard deviation of 2.2 incontinence episodes/day. Based on these assumptions, a sample size of 93 subjects would be required to demonstrate a statistically significant reduction from baseline. To account for an attrition of approximately 20% during the course of the study, a sample size of up to 120 subjects is required for this study.

The sample size requirement of 93 for the primary objective is also adequate to assess the secondary objectives of number of voids per day and quality of life measured by OABq. In the OrBIT trial by Peters et al (2009)⁵, the average reduction of voids at 12 weeks compared to baseline in the PTNS arm was 2.4 voids per day with a standard deviation of 4.0. Based on a one-sample t-test, with $\alpha=0.05$ two-sided, 90% power, 44 subjects with UF are required to demonstrate a statistically significant reduction from baseline if using a conservative estimate of a reduction of 2.0 voids per day with a standard deviation of 4.0. In the InSite study, among all implanted subjects 63% of the urinary incontinence (UI) subjects had both UI and UF at baseline.²⁹ Therefore, 93 subjects should ensure the sample size needed for the secondary objective of UF based on this assumption.

In the OrBIT trial by Peters et al (2009)⁵, the average improvement from baseline of HRQL from OABq for PTNS at 12 weeks was 25.3 ± 21.5 . Based on a one-sample t-test, with $\alpha=0.05$ two-sided, 90% power, 15 subjects are required to demonstrate a statistically significant reduction from baseline when using a conservative estimate of average improvement of 20 points at 12 weeks with a standard deviation of 22. Therefore, 93 subjects should ensure the sample size need for the secondary objective of OABq.

Confidential

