7.9.3.4. Patient reported outcomes

- Self-Assessment Goal Achievement Questionnaire (SAGA)

Objective:

To summarize SAGA first visit at baseline and SAGA follow-up collected at final visit after 12th PTNM session for subjects who receive PTNM therapy.

Endpoint definition:

The SAGA questionnaire asks subjects to rank, in order of importance for standard urology symptom goals using a scale of 0-5 and allows for other personal goals to be included³. In SAGA follow-up assessment, it includes a scale of -2 to 2 to report on achievement of each symptom goal and other personal goal(s). The questionnaire includes an assessment question of "Overall, to what extent have you achieved your goals" on a scale of 0-4.

Data collection and analysis methods:

SAGA data are collected for baseline (goal-assessment; ranking) and follow-up (goal-achievement) after the 12th session.

SAGA data will be analyzed for subjects who receive the PTNM therapy and have data at baseline and follow-up after the 12th session. Baseline data will be summarized by importance of symptom goals for

each fixed symptom goal. Number of subjects and percent of subjects in each rating from not very important to very important for each fixed goal will be reported.

In the SAGA follow-up, SAGA goal achievement for each fixed goal will be tabulated from much worse than expected to much better than expected. The assessment on overall question on goal achievement will be summarized from “Did not achieve my goals at all” to “Exceeded my goals”.

For the SAGA follow-up, goal attainment scores will be calculated according to the formula provided by Kiresuk and Sherman⁴ (T-scores with mean=50 and SD=10) for 9 fixed goals. Additionally, weights will be applied to goal achievement ratings based on the baseline level of importance attached to each goal. Descriptive statistics for the T-scores will be reported. A mean T-score of 50 represents an outcome of goal achievement. Scores>50 are interpreted as exceeding goal and scores <50 as only somewhat or partially achieving goal⁵.

Determination of subjects for analysis:

All qualified subjects who receive PTNM therapy with both SAGA first and SAGA follow-up data will be included in the analysis.

- Patient Perception of Bladder Condition (PPBC)

Objective:

To summarize PPBC at baseline and by PTNM sessions for subjects who receive PTNM therapy.

Endpoint definition

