PPBC is a 6-point scale to describe the subject's bladder condition from bladder condition not causing problem to causing many severe problems.

Data collection and analysis methods

PPBC data are collected for baseline and the 1st, 4th, 8th and 12th PTNM sessions. Number of subjects and percent of subjects in each condition of the scale will be summarized by visit.

Determination of subjects for analysis

All subjects who are treated by the PTNM therapy and have data available will be included in this analysis.

- Patient Global Impression of Improvement (PGI-I)

Objective:

To summarize PGI-I collected at the end of the study.

Endpoint definition

PGI-I is a single question asking the patient to rate their urinary condition as compared with prior to beginning treatment on a scale from 1 (very much better) to 7 (very much worse).

Data collection and analysis methods

This questionnaire is collected following the 12th PTNM session. Number of subjects and percent of subjects in each of 7 categories will be presented for subjects with data available, especially the number and percent of subjects who report “Very much better” and “Much better” will be provided.

Furthermore, three categories with “Very much better” and “Much better”, “A little better” combining into “Better”; “No change” as “Same”; and “A little worse”, “Much worse”, and “Very much worse” combining into “Worse” will be analyzed. Additionally, descriptive statistics including mean, standard deviation, and median will be provided.

Determination of subjects for analysis

All qualified subjects who receive PTNM therapy and have data available will be included in this analysis.

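### No exit assessment is scheduled for treated subjects who stop early: PGI-I and SAGA omit them, and those who leave without attending another visit have no scheduled adverse-event review after their last session

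*Protocol*

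**What the plan says.** **Withdrawal.** Protocol 10.10 says: "When a subject is withdrawn from the study, the Study Discontinuation eCRF is to be completed and should include detailed notes as to why" they left, and gives discomfort and lack of efficacy among its example reasons. It names no questionnaire, diary or adverse-event (AE) review at exit. Table 1-1 runs from baseline through twelve sessions to the Final Study Visit and has no early-exit column. (Figure 1-1 was not available in the text I worked from.)

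**PGI-I and SAGA.** Table 1-1 places PGI-I at the Final Study Visit only, and SAGA at baseline and the Final Study Visit. SAP 7.9.3.4 says of PGI-I: "This questionnaire is collected following the 12th PTNM session". It summarises PGI-I in treated subjects who have a rating and singles out the top two categories. On SAGA it says: "SAGA data will be analyzed for subjects who receive the PTNM therapy and have data at baseline and follow-up after the 12th session".

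**Early leavers elsewhere.** For UUI, SAP 7.9.1 plans an adjusted worst-case analysis. Subjects who withdraw because of related AEs or unsuccessful treatment are given their baseline value, and other leavers have their last observation carried forward. SAP 7.9.2 extends this to the secondary objectives. Nothing similar is planned for the additional measures.

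**AE review.** Protocol Section 10 says: "At the weekly follow-up visits, any OAB medication(s), conservative therapies for OAB and reportable adverse events will be collected from the subject". That day's therapy follows, and the Synopsis gives the same order. SAP 7.9.3.1 uses all qualified treated subjects as the AE denominator.

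**The concern.** PGI-I and the SAGA follow-up have no earlier post-baseline value, so carrying an observation forward is impossible. A subject who stops because the treatment hurts or does not help disappears from both summaries. The plan treats that same subject as unimproved in the sensitivity analyses for UUI, voids and OABq. In a single open-label arm no comparator shares this selection, and the proportion in the top PGI-I categories is the figure most likely to be read as a statement about treated patients.

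For safety, the visit order means that a session is asked about at the next visit. A subject who never attends another visit is not scheduled to be asked about the last session, but still counts in the denominator of the related-AE incidence. The study has no data monitoring or events committee (Protocol 13), so the safety summary rests on what sites report.

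**Working it through.** **1. The plan's own figure.** Inputs from Protocol 14.1.1: "reduction of 0.75 UUI episodes/day from baseline, one-sample t-test with two-sided $\alpha=0.05$, 90% power" and "an estimated standard deviation of 2.2 incontinence episodes/day". With λ = (0.75/2.2)√n, the power of the two-sided one-sample t-test is P(|T| > t(0.975, n−1)), where T is noncentral t with n−1 degrees of freedom and noncentrality λ. The smallest n with power of at least 0.90 is **93** (λ = 0.3409 × √93 = 3.29), which matches the plan. The normal approximation gives (2.2 × 3.2415/0.75)² = 90.4, so 91.

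**2. How many leavers the plan allows for.** Protocol 14.1.1 says: "To account for an attrition of approximately 20% during the course of the study, a sample size of up to 120 subjects is required".
- 93/(1 − 0.20) = 116.25, so 117; the plan uses 120.
- 20% of 120 = **24** leavers, with 96 remaining.
- If only 93 remain, 120 − 93 = **27** leavers, which is 22.5%.

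**3. PGI-I bounds over all treated subjects.** Let N = 120, m = number missing and p = the rate among those with a rating. This takes all 120 as treated and all m as lacking a rating.
- Lower bound (no missing subject improved): p(N − m)/N.
- Upper bound (every missing subject improved): [p(N − m) + m]/N.
- Width: m/N = 24/120 = **20 points**, or 27/120 = **22.5 points**, whatever p is.

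The values of p below are assumptions; the documents give none.

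| p | m = 24 | m = 27 |
|---|---|---|
| 40% | 32% to 52% | 31% to 53.5% |
| 60% | 48% to 68% | 46.5% to 69% |
| 70% | 56% to 76% | 54.25% to 76.75% |

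**4. Direction.** If leavers improve at rate q, the reported rate exceeds the all-treated rate by (m/N)(p − q). This is zero when q = p and positive only when q < p. The example reasons in Protocol 10.10 make q < p plausible, but the documents give no value for q.

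**5. SAGA.** The SAP reads a mean T-score of 50 as goal achieved. As an illustration, assume a mean of 52 among 96 subjects with follow-up. If the 24 leavers would average 40, the all-treated mean is (52 × 96 + 40 × 24)/120 = 49.6; if they would average 45, it is 50.6. A modest completer result could fall on either side of 50.

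**6. AE review.** Because review precedes therapy, session k is reviewed at the visit for session k + 1, and session 12 at the final visit. Let f be the share of leavers who never attend another visit after their last session. The number with no scheduled review of that session is f × m:
- f = 0: 0
- f = 0.5: 12 to 13.5
- f = 1: 24 to 27, which is 20% to 22.5% of 120

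The documents do not give f.

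**The case against.** **Importance.** PGI-I and SAGA are additional measures, summarised descriptively with no hypothesis test. The SAP states openly who is included, and SAP 7.1.1 reports disposition and reasons for discontinuation by visit, so a reader can see the attrition. The primary and secondary objectives do have a planned analysis for leavers. All of this stands and limits the weight of the point. It does not explain why the rule used for the other outcomes has no counterpart here.

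**Adverse events.** A reader might infer that every early leaver's last session goes unreviewed. The documents do not support that. A subject who attends the next visit and withdraws there before treatment has been reviewed, and so has one who misses session 12 but attends the final visit. Protocol 11.1.2 also instructs monitoring during the session. Protocol 12.2 gives the investigator a general duty to identify reportable events. Protocol 10.10 asks for the reason for withdrawal, and for at least three contact attempts before a subject is deemed lost. An event known to have caused an exit should therefore be captured. What remains is narrower: none of these is a scheduled AE enquiry after the last session, and the contact attempts specify no AE question.

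**Size.** The 20% is a general allowance. It may include qualified subjects who exit before session 1, or who lack only a usable diary. A reader might also assume a 70% completer rate, suppose that at most 40% of leavers improved, and conclude that the true rate is 56% to 64%: (0.70 × 96 + 0)/120 and (0.70 × 96 + 0.40 × 24)/120. That cap builds in the answer; without it the range is 56% to 76%. Reasons such as pregnancy, illness or diary burden need not reflect poor response.

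**Remedy.** Questionnaires are self-completed on paper without site consultation (Protocol 10.6 and 10.8), so a telephone PGI-I would conflict with the plan. Pooling early exit ratings with ratings after session 12 would mix timepoints. Both objections are right, and the fix respects them.

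**Conclusion.** The gap is real in this form. No assessment is scheduled for treated subjects who stop early, and PGI-I and SAGA follow-up describe only those who reach the final visit, with no sensitivity analysis. Under the plan's own attrition allowance, 20% to 22.5% of subjects may be missing, and the all-treated PGI-I rate is then known only to within 20 to 22.5 points. Upward bias is likely if leavers did worse, as the plan's own worst-case rule supposes, but its size cannot be taken from the documents.

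On safety, the supported statement covers only subjects who leave without attending another visit: between 0 and about 24 to 27 of 120. A reader should not conclude that 24 subjects lack AE review, or that the related-AE incidence is biased downward by a known amount. Under-ascertainment is possible; its extent is not determined.

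The figures assume that all 120 are treated, that attrition matches the allowance, and that attrition means not reaching the final visit. The primary analysis is not in question. I would class this as a cheap improvement.

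**What to change.** **Protocol 10.10 and Table 1-1.** Add an early-exit assessment for any subject who has had at least one PTNM session and stops. Use the existing Final Study Visit items where the subject is willing: AE and OAB medication review, OABq, UPS, PPBC, PGI-I, SAGA and a 3-day diary. If attendance is declined, carry out at least the AE review by telephone. Any PGI-I should still be self-completed on paper.

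**SAP 7.9.3.4.** Keep the post-session-12 summaries as they are. Report exit PGI-I and SAGA values separately, with the number missing. Add a sensitivity summary of the top two PGI-I categories (very much better, much better) over all treated subjects, counting missing as not improved. This mirrors the treatment-failure part of the worst-case rule in SAP 7.9.1.

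**Cost.** The protocol part needs an amendment with IRB approval (Protocol 16.6) across about 15 sites. Some leavers will decline, and the added summary will show a somewhat lower improvement rate. The SAP part uses existing forms and is separable: the number missing and the all-treated PGI-I summary can be added even if the protocol is not amended.
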